5.3. Rescreening

Individuals who do not meet the criteria for participation in this study (screen failure) may be re-screened, only after discussion with and permission from the Lilly CRP or designee.

Repeating laboratory tests during the screening period does not constitute re-screening. Screening laboratory tests may not be repeated more than twice in order to meet eligibility during the screening period.

6. Treatment

6.1. Treatments Administered

Ramucirumab and pembrolizumab will be administered per [Table JVDF.2](#). For Gastric/GEJ, Urothelial, 2nd-4th line NSCLC and BTC, patients can receive study treatment after evaluable tumor tissue has been shipped to central study laboratory. For first line NSCLC, patient can receive study treatment after PD-L1 expression has been confirmed to be at least 1% (Section [5.1](#)).

Across all study periods, including the continued access period, individual patients will be treated with ramucirumab and/or pembrolizumab, as follows:

- until confirmed progressive disease (Section [8.1.1.3](#)), unacceptable toxicity, or discontinuation for any other reason
- for a maximum duration of study treatment of 35 cycles, approximately 2 years

Table JVDF.2. Phase 1 Treatment Regimens/Dosing Schedule

Tumor Type	Drug	Dose (IV)	Dose Frequency	Dose Day (21-day cycle)
Schedule 1 (Gastric-GEJ, BTC)	Ramucirumab	8 mg/kg	Q3W	Day 1, Day 8
	Pembrolizumab	200 mg	Q3W	Day 1
Schedule 2 (Gastric-GEJ, NSCLC or Urothelial)	Ramucirumab	10 mg/kg	Q3W	Day 1
	Pembrolizumab	200 mg	Q3W	Day 1

Abbreviations: BTC = biliary tract cancer; GEJ = gastroesophageal junction; IV = intravenous; NSCLC = non-small cell lung cancer; Q3W = every 3 weeks.

NOTE: Ramucirumab will be administered prior to pembrolizumab for every cycle (Section [6.1.1](#)).

6.1.1. Selection and Timing of Doses

The ramucirumab and the pembrolizumab Pharmacy Manuals contain specific instructions for premedication, the preparation of infusion, and administration of each infusion solutions, separately.

A cycle is defined as an interval of 21 days (a delay of a cycle due to holidays, weekends, bad weather, or other unforeseen circumstances will be permitted up to 7 days and not counted as a protocol deviation).

The actual doses of ramucirumab administered will be determined by measuring the patient's weight at the beginning of each cycle. If the patient's weight fluctuates by more than $\pm 10\%$ from the weight used to calculate the prior dose, the dose must be recalculated. Recalculation of the ramucirumab dose for weight fluctuations of $<10\%$ is permitted but not required.

Ramucirumab will be administered prior to pembrolizumab, over an approximately 60-minute intravenous (IV) infusion. The maximum ramucirumab infusion rate is 25 mg/min.

Pembrolizumab 200 mg (fixed dose) will be administered over a 30-minute IV infusion. Sites should make every effort to target infusion timing to be as close to 30 minutes as possible. However, given the variability of infusion pumps from site to site, a window between -5 minutes and +10 minutes is permitted (that is, infusion time is 30 minutes -5 min/+10 min).

The first 2 cycles will require a 1-hr observation period i) between ramucirumab and pembrolizumab administration, and ii) after pembrolizumab infusion. For all cycles thereafter, no observation period will be required unless clinically indicated.

6.1.1.1. Phase 1a: Dose-Limiting Toxicity Observation

For the 21-day Phase 1a DLT observation period, the following criteria will be used to determine the progress of the study:

- If none of the initial 3 patients within a dose schedule develops a DLT, Expansion Phase 1b will start.
- If 1 of the initial 3 patients within a dose schedule develops a DLT, 3 additional patients will be added.
- If ≤ 1 of 6 patients within a dose schedule develops a DLT, Expansion Phase 1b will start.
- If 2 or more patients develop a DLT, enrollment will stop and an alternative dose level may be considered (in which case the protocol would be amended).

No intra-patient dose escalation or reduction is allowed during DLT observation. For the purpose of patient management, DLTs will lead to dose interruption during the observation period. Dose modifications will be allowed after the observation period.

For either group, if dropouts, dose interruptions, or reductions occur that result in a patient being nonevaluable for DLTs (“evaluable” is defined in Section 6.7), additional patients will be enrolled to achieve the minimum of 3 evaluable patients. The need for patient replacement will be determined based on consultation with the investigator and Lilly CRP/clinical research scientist (CRS). Patients who withdraw from the study during the DLT period for reasons other than a DLT may be replaced within the same dose level.

6.1.1.1.1. Definition of Dose-Limiting Toxicities

A DLT is defined as one of the following AEs reported during the DLT observation period, if considered to be definitely, probably, or possibly related to either study regimen by the investigator; and fulfills any one of the following criterion using NCI CTCAE Version 4.0:

1. Nonhematologic toxicity as follows:
 - a) Grade 4 nonlaboratory toxicity
 - b) Grade 3 nonlaboratory toxicity (for example, nausea, vomiting, and diarrhea) lasting >3 days despite optimal supportive care
 - c) Any Grade 3 or Grade 4 laboratory value if:
 - i) Medical intervention is required to treat the patient, or
 - ii) The abnormality persists for >1 week.

Note: Liver function abnormality: For patients with liver metastasis who begin treatment with Grade 2 asparatate aminotransferase (AST) or alanine amino transferase (ALT), if AST or ALT increases by greater than or equal to 50% relative to baseline and lasts for at least 7 days

2. Hematologic toxicity, as follows:
 - a) Grade 4 toxicity lasting \geq 7 days, or
 - b) Grade 3 thrombocytopenia if associated with bleeding and requires platelet transfusion, or
 - c) Febrile neutropenia Grade 3 or Grade 4
3. Grade 5 toxicity (that is, death)
4. Any other significant toxicity deemed by the primary investigator and Lilly clinical research personnel to be dose limiting, for example:
 - a) Any toxicity that is possibly related to study treatment that requires the withdrawal of the patient from the study during Cycle 1, or
 - b) A delay of $>$ 14 days due to persistent Grade \geq 2 toxicities in initiating Cycle 2, with the exception of Grade 2 fatigue

Any infusion or hypersensitivity reactions occurring during the infusion of the drug are not considered dose-related and therefore will NOT be considered to be a DLT.

After each of the 3 patients in a dose schedule completes the observation period, a safety analysis will occur; the data will be reviewed by study investigators and the Lilly CRP/CRS, and the findings documented, indicating whether each dose schedule is or is not well tolerated. The results will inform the decision whether or not to move onto Expansion Phase 1b.

6.1.2. *Investigator Responsibilities*

The investigator or his/her designee is responsible for the following:

- explaining the correct use of the drugs and planned duration of each individual's treatment to the site personnel,
- verifying that instructions are followed properly,
- maintaining accurate and appropriate records, including those of investigational product (IP) dispensing and collection,
- ensure appropriate supply, storage, handling, distribution and usage of trial treatments in accordance with the protocol and any applicable laws and regulations,
- and returning all unused medication to Lilly or its designee at the end of the study.

Note: In some cases, sites may destroy the material if, during the investigator site selection, the evaluator has verified and documented that the site has appropriate facilities and written procedures to dispose clinical trial materials.

Patients will be instructed to contact the investigator as soon as possible if they have a complaint or problem with the IP so that the situation can be assessed.

6.2. Treatment Assignment

Patients meeting all inclusion/exclusion criteria will be assigned to a dose schedule based upon their diagnosis at baseline ([Table JVDF.2](#)). Study drug will be allocated to patients using an interactive web response system.

6.3. Blinding

This is an open-label study.

6.4. Packaging and Labeling

All IP materials will be provided by Lilly. Clinical trial materials will be labeled according to the country's regulatory requirements. Ramucirumab and pembrolizumab vials should be stored under refrigeration at 2°C to 8°C (36°F to 46°F).

6.5. Preparation/Handling/Storage

Refer to the respective IBs for detailed information about preparation, handling, and storage of ramucirumab and pembrolizumab.

6.6. Dose Adjustments, Delays, and Discontinuation

Doses of either study drug may need to be delayed, reduced (ramucirumab only), or discontinued to manage specific AEs or other toxicities.

When a study drug is delayed, if possible and appropriate, patients should resume study treatment within 21 days, with every effort made to start on Day 1 of the next dosing schedule.

6.6.1. Ramucirumab Dose Adjustments, Delays, and Discontinuation

The ramucirumab dose may need to be delayed and/or reduced if the patient experiences an adverse event, including an adverse event of special interest (AESI) (Section [8.2.1.1.1](#)). Doses may be delayed to allow time for the patient to recover from the event. Certain AEs require immediate and permanent discontinuation of study treatment. Any patient who requires a dose reduction will continue to receive a reduced dose until discontinuation from ramucirumab or discontinuation from the study. Any patient who has had 2 dose reductions and who experiences a toxicity that would cause a third dose reduction must be discontinued from ramucirumab.

[Table JVDF.3](#) presents the ramucirumab dose reductions for each treatment cohort.

[Table JVDF.4](#) presents the criteria for dose modifications and dose discontinuations applicable if the patient experiences a ramucirumab AESI or other AEs at least possibly related to ramucirumab.

Table JVDF.3.

Ramucirumab Dose Reductions^a

	Dose Schedule 1: Gastric-GEJ/BTC (21-day Cycle)	Dose Schedule 2: Gastric-GEJ/NSCLC/Urothelial (21-day Cycle)
Starting dose	8 mg/kg on D1, D8	10 mg/kg on Day 1
First dose reduction	6 mg/kg on Day 1, Day 8	8 mg/kg on Day 1
Second dose reduction	5 mg/kg on Day 1, Day 8	6 mg/kg on Day 1

Abbreviations: BTC = biliary tract cancer; D = Day; GEJ = gastroesophageal; NSCLC = non-small cell lung cancer.

^a Ramucirumab dose reductions are allowed between cycles and within a given cycle.

Table JVDF.4. Dose-Modification Guidelines for Ramucirumab for Adverse Events at Least Possibly Related to Ramucirumab, including Adverse Events of Special Interest

Adverse Event NOTE: All Specific Adverse Events Listed are defined as AESIs in Section 8.2.1.1.1).		CTCAE Grade	Dose-Modification Guidelines NOTES: Dose reductions to occur as defined in Table JVDF.3. Treating physicians can modify or discontinue ramucirumab more conservatively than in the guidance below.
1.	Infusion-related reaction		
1.a.	Infusion-related reaction	2	
Interrupt and reduce the infusion rate by 50% for the duration of the infusion and for all future infusions.
 
Prior to all future infusions of ramucirumab, premedicate with:
 
 • an intravenous histamine H1 antagonist, such as diphenhydramine hydrochloride • dexamethasone or equivalent • acetaminophen/paracetamol
1.b.	Infusion-related reaction	3-4	Immediately and permanently discontinue ramucirumab
2.	Hypertension		
2.a.	Hypertension (non-life-threatening and associated with symptoms) NOTE: Hypertension should be monitored prior to each ramucirumab infusion.	3	
 • Delay ramucirumab until the hypertension is controlled with medication and is resolved to Grade 0-2. 
 ◦ If controlled with medication and resolved to Grade 0-2, then may resume ramucirumab at current dose. ◦ If NOT controlled with medication and not resolved to Grade 0-2 within a reasonable timeframe, discontinue ramucirumab at investigator's discretion.
2.b.	Uncontrolled hypertension, hypertensive crisis, or hypertensive encephalopathy	4	Immediately and permanently discontinue ramucirumab.

Dose-Modification Guidelines for Ramucirumab for Adverse Events at least Possibly Related to Ramucirumab, including Adverse Events of Special Interest (continued)

	Adverse Event NOTE: All Specific Adverse Events Listed are defined as AESIs in Section 8.2.1.1.1.	CTCAE Grade	Dose-Modification Guidelines NOTE: Dose reductions to occur as defined in Table JVDF.3.
3.	Proteinuria		
3.a.	Proteinuria = 2+ (dipstick or routine urinalysis) ^a		
 Administer ramucirumab at the current dose if clinically indicated. Obtain 24-hour urine protein results within 3 days prior to the next ramucirumab dose. 
 If urine protein is <2 g/24 h, administer ramucirumab at the patient's current dose. If urine protein is ≥2 g/24 h, modify the ramucirumab dose based on 24-hour collection. See Proteinuria ≥2 g/24 h (24-hour urine collection), Line 3.c in this table.
3.b.	Proteinuria >2+ (dipstick or routine urinalysis) ^a		
 Delay ramucirumab until urine protein returns to <2 g/24 h. Obtain 24-hour urine protein results within 3 days prior to the next ramucirumab dose. 
 If urine protein is <2 g/24 h, no further dose delay or dose reduction is required. If urine protein remains ≥2 g/24 h and is not resolved within a reasonable timeframe, discontinue ramucirumab at investigator's discretion.
3.c.	Proteinuria ≥2 g/24 h (24-hour urine collection) ^a		
 First or second occurrence: delay ramucirumab until urine protein returns to <2 g/24 h. 
 If urine protein returns to <2 g/24 h, reduce ramucirumab dose. If urine protein remains ≥2 g/24 h and is not resolved within a reasonable timeframe, discontinue ramucirumab at investigator's discretion. Third occurrence: discontinue ramucirumab.
3.d.	Proteinuria >3 g/24 h or in the setting of nephrotic syndrome ^a		Immediately and permanently discontinue ramucirumab.
4.	Arterial thromboembolic events, venous thromboembolic events	3 or 4	Immediately and permanently discontinue ramucirumab.
5.	Bleeding/hemorrhage	3 or 4	Immediately and permanently discontinue ramucirumab.
6.	Gastrointestinal perforation		Immediately and permanently discontinue ramucirumab.

	Adverse Event NOTE: All Specific Adverse Events Listed are defined as AESIs in Section 8.2.1.1.1).	CTCAE Grade	Dose-Modification Guidelines NOTE: Dose reductions to occur as defined in Table JVDF.3.
7.	Reversible posterior leukoencephalopathy syndrome		Immediately and permanently discontinue ramucirumab.
8.	Congestive heart failure	3-4	Immediately and permanently discontinue ramucirumab.
9.	Fistula formation		Immediately and permanently discontinue ramucirumab.
10.	Impaired wound healing		
10.a.	Prior to planned surgery		Withhold ramucirumab.
10.b	After surgery		Resume ramucirumab based on clinical judgment.
10.c.	Wound-healing complications developed during study treatment		Delay ramucirumab dosing until the wound is fully healed.
11.	Liver injury/liver failure		
11.a.	Hepatic encephalopathy and/or hepatorenal syndrome resulting from liver cirrhosis		Immediately and permanently discontinue ramucirumab.
12	Hypothyroidism	2-4	Therapy with ramucirumab can be continued while treatment for the thyroid disorder is instituted.
13	Other adverse events considered at least possibly related to ramucirumab^b		
13.a	Non-life threatening and reversible	3	
May delay ramucirumab until resolved to Grade 0-1.
 
 • If resolved to Grade 0-1, may reduce ramucirumab dose. • If NOT resolved to Grade 0-1 within a reasonable timeframe, discontinue ramucirumab at investigator's discretion
13.b	Adverse Event	4	
Permanently discontinue treatment immediately, with the exception of Grade 4 fever or Grade 4 laboratory abnormality, in which case:
 
 • First occurrence: Delay ramucirumab until resolved to Grade 0-1. 
 ◦ If resolved to Grade 0-1, may resume ramucirumab original dose at the discretion of the investigator. ◦ If NOT resolved to Grade 0-1 within a reasonable timeframe, discontinue ramucirumab at investigator's discretion. • Second occurrence: Delay ramucirumab until resolved to Grade 0-1. 
 ◦ If resolved to Grade 0-1, reduce ramucirumab dose. ◦ If NOT resolved to Grade 0-1 within a reasonable timeframe, discontinue ramucirumab at investigator's discretion.

Dose-Modification Guidelines for Ramucirumab for Adverse Events at least Possibly Related to Ramucirumab, including Adverse Events of Special Interest (concluded)

Abbreviations: AESI = adverse event of special interest; CTCAE = Common Terminology Criteria for Adverse Events; NCI = National Cancer Institute.

- a Perform urinalysis within 3 days prior to each infusion of ramucirumab. If 24-hour urine collection is also performed, the results of 24-hour urine collection should be used for clinical decision-making.
- b Patients who enter the study with symptoms or laboratory values equivalent to NCI-CTCAE Version 4.0 Grade 1-2 adverse events should not necessarily have dose delays or reductions related to the persistence or mild worsening of those symptoms or laboratory values. Grade 2 toxicities which represent clinically significant worsening of symptoms from baseline, ramucirumab dose may be delayed at the discretion of the investigator. If the toxicity is resolved to Grade 0-1, may reduce ramucirumab dose. If the toxicity is not resolved to Grade 0-1, may discontinue ramucirumab.

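### For dipstick protein above 2+ with a 24-hour value of 2 to 3 g, Table JVDF.4 line 3.b requires no ramucirumab reduction after recovery, while line 3.c requires one

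*Protocol*

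**What the plan says.** Protocol 6.6.1, Table JVDF.4, handles proteinuria in four lines.

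- **3.a, dipstick equal to 2+.** The next dose may go ahead: "Administer ramucirumab at the current dose if clinically indicated". A 24-hour collection follows. If it shows 2 g or more, the site is told to "modify the ramucirumab dose based on 24-hour collection" and is referred by name to line 3.c.
- **3.b, dipstick above 2+.** The drug is held: "Delay ramucirumab until urine protein returns to <2 g/24 h". The site must also "Obtain 24-hour urine protein results within 3 days prior to the next ramucirumab dose". There are two branches. Below 2 g/24 h, "no further dose delay or dose reduction is required". The other begins "If urine protein remains ≥2 g/24 h and is not resolved within a reasonable timeframe" and leaves discontinuation to the investigator. Neither branch refers to another line.
- **3.c, 24-hour protein of 2 g or more.** There is no dipstick condition. At a first or second occurrence the drug is held to the same threshold, and then: "If urine protein returns to <2 g/24 h, reduce ramucirumab dose". A third occurrence ends ramucirumab.
- **3.d, more than 3 g/24 h, or nephrotic syndrome.** Ramucirumab stops for good. Section 6.9.1.2.1.2 repeats this.

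Footnote a is attached to all four lines and says that a 24-hour result, where there is one, should guide the decision. Attachment 1 schedules a 24-hour analysis for dipstick above 2+ on treatment, and Attachment 3 (footnote b) makes the collection mandatory from 2+ upward. A note in the table lets physicians be more cautious than its guidance.

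**The concern.** One patient can meet two lines that disagree on the dose after recovery. With the same 24-hour value, a patient at exactly 2+ is sent expressly to 3.c and must be reduced, while a patient with a worse dipstick is not sent there and can be read as needing no reduction. The table gives no reason for this inversion.

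Proteinuria is a listed ramucirumab adverse event of special interest (SAP 5.2.1.3), and safety and tolerability is the primary objective. Section 6.6.1 makes reductions permanent and allows two. A toxicity that would cause a third ends ramucirumab, whatever the toxicity. Which line a site follows therefore affects the current dose and also how close the patient is to that limit. SAP 5.3.6 summarises dose modifications and dose intensity, so those summaries would partly reflect how each site read the table.

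**Working it through.** The plan gives no figure for this conflict. The check sets the lines side by side and then works out the doses.

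**1. Where the lines overlap.** Line 3.b starts at dipstick above 2+. Line 3.c starts at 2 g/24 h whatever the dipstick. Line 3.d takes over above 3 g or with nephrotic syndrome. The overlap is dipstick above 2+ with 24-hour protein from 2 g up to and including 3 g, without nephrotic syndrome.

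**2. Whether 3.b covers only patients below 2 g.** Its wording does not fit that. A value can *return* to below 2 g, or *remain* at 2 g or more, only if it was at 2 g or more before.

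**3. One episode: dipstick above 2+, 24-hour protein 2.5 g, later 1.5 g.**

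| | Line 3.b | Line 3.c |
|---|---|---|
| At 2.5 g | hold | hold |
| At 1.5 g | no reduction required | reduction required |

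**4. Dose after recovery, from the starting dose.** The inputs are the dose steps in Table JVDF.3 and a 21-day (3-week) cycle. The formulas are: dose per cycle = infusions × mg/kg; weekly intensity = dose per cycle / 3.

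- Schedule 1, unreduced: 2 × 8 = 16 mg/kg; 16/3 = 5.33 mg/kg/week. SAP 5.2.1.2 plans 5.3, so the calculation reproduces it.
- Schedule 1, first reduction: 2 × 6 = 12 mg/kg; 12/3 = 4.00 mg/kg/week; 12/16 = 75% of plan.
- Schedule 2, unreduced: 10 mg/kg; 10/3 = 3.33 mg/kg/week. SAP 5.2.1.2 plans 3.3, again reproduced.
- Schedule 2, first reduction: 8 mg/kg; 8/3 = 2.67 mg/kg/week; 8/10 = 80% of plan.

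The reduction that 3.c requires and 3.b does not is thus 25% in Schedule 1 and 20% in Schedule 2. Stated relative to the reduced dose, a site following 3.b alone gives 16/12 = 1.33 or 10/8 = 1.25 times as much.

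**5. Patients already reduced.** After one earlier reduction, the comparison is 2 × 6 = 12 against 2 × 5 = 10 mg/kg per cycle in Schedule 1 (10/12 = 83%), and 8 against 6 mg/kg in Schedule 2 (6/8 = 75%). After two, the reduction under 3.c would be the third, so Section 6.6.1 stops ramucirumab. Line 3.b read alone would let the patient continue at 10 or 6 mg/kg per cycle.

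**The case against.** The strongest reply is that the protocol already settles the matter. Attachment 3 makes the 24-hour collection mandatory for everyone in the disputed group, and footnote a says its result should guide the decision. Line 3.c is triggered by that result alone. Line 3.d also applies to these patients without any pointer from 3.b, so the 24-hour lines appear to be free-standing. The two lines are also compatible: 3.b says that a reduction is not required, not that it is forbidden, so reducing the dose satisfies both.

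Most of this stands as evidence of intent: 3.c should govern. It does not remove the problem. The branches of 3.b themselves use 24-hour values, so a site following them can believe that it has complied with footnote a. The footnote does not say that 3.c overrides 3.b. The stop above 3 g has a second text behind it in Section 6.9.1.2.1.2; the reduction at 2 to 3 g has none. The note on caution permits a reduction but does not require it.

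Three stronger readings are tempting, and the documents do not support them.

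- *Line 3.b restores the full dose.* It leaves the dose unchanged, so an already reduced patient resumes at the reduced level.
- *An episode handled under 3.b escapes the three-occurrence rule.* Line 3.c counts any 24-hour value of 2 g or more, and nothing in 3.b suspends that count. What a literal reading omits is the reduction itself.
- *Line 3.b is laxer throughout.* At first it is stricter than 3.a, because it holds the drug at once while 3.a allows a dose before the 24-hour result.

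**Conclusion.** The conflict is real but narrow. It concerns only the ramucirumab dose at resumption, for dipstick above 2+ with 24-hour protein of 2 to 3 g and no nephrotic syndrome. Line 3.c is the likely intent, but 3.b as worded can be followed to a different result. From the starting dose, one episode leaves the patient on 16 instead of 12 mg/kg per cycle (Schedule 1) or 10 instead of 8 mg/kg (Schedule 2), with none rather than one of the two permitted reductions used.

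These figures assume that the site applies 3.b on its own, that the episode is a first or second occurrence, and that protein falls below 2 g/24 h. The documents do not say how often this combination arises, so the number of patients affected cannot be estimated. A reader might infer a threat to the study's statistical design. There is none: sample size, power and alpha do not depend on this rule, and exposure is summarised descriptively. The point is worth correcting because it bears on management of a known toxicity and the correction is small.

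**What to change.** In Table JVDF.4 line 3.b:

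1. Keep the immediate hold.
2. Require the 24-hour collection promptly after each dipstick above 2+. The present window of 3 days before the next dose is not enough by itself: with the drug held, the only result could come after recovery and hide a value of 2 g or more. Tying the rule to the collection prompted by each dipstick also makes it clear for repeat episodes.
3. Replace the two sub-branches with:
   - If the 24-hour collection prompted by this dipstick is <2 g/24 h, "no further dose delay or dose reduction is required".
   - If it is ≥2 g/24 h, modify the dose per Line 3.c (or Line 3.d if >3 g/24 h or nephrotic syndrome).

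This gives 3.b the link that 3.a already has and agrees with footnote a. The existing branch for protein that stays at 2 g or more can go, because 3.c contains it.

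The cost is a wording change in one table line, plus explicit timing for a collection that Attachments 1 and 3 already call for. The downside is possibly some additional ramucirumab reductions, which 3.c already requires; their number is unknown. Sample size, power and alpha do not change.
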